13.2.1 Reporting Requirements for Serious Adverse Events

Initial Reporting

SAEs (based on FDA/ICH definition of an SAE) require immediate reporting to Mallinckrodt or designated representative.

For all fatal or life-threatening events, the investigator(s) or designee must report information within 24 hours to the Medical Monitor at [contact].

For all SAEs, the investigator(s) or designee must complete the SAE report form with the minimum information required by FDA and ICH and fax it to Mallinckrodt Pharmacovigilance at [contact] within 24 hours of first knowledge of the event even if the experience does not appear to be related to the study drug.

The investigator(s) or designee will receive acknowledgement of receipt of the SAE report form from Mallinckrodt.

Should the investigator(s) or designee have any difficulty in sending the SAE report, they may contact Mallinckrodt Pharmacovigilance at [name] (24 hour call center) or email: [contact].

If there is any doubt about whether the information constitutes an SAE, the information is to be treated as an SAE.

Follow Up Reporting

The investigator(s) or designee must complete an SAE report form for all follow-up information received and fax it to the sponsor [contact] within 24 hours of receipt of additional or updated information (eg, detailed written descriptions that include copies of relevant subject records, autopsy reports and other supporting documents). The investigator(s) or designee will receive acknowledgement of receipt for each SAE report form from Mallinckrodt.

The investigator(s) or designee is required to report immediately unexpected SAEs to the responsible IRB/IEC.

All adverse events (serious and non-serious) occurring in subjects from the time of informed consent through the completion of the follow-up telephone call will be documented as an AE in the source and in the eCRF. All fields on the AE eCRF page should be completed for each event with a full description of the event and date and time of onset and resolution. The investigator must follow up on all AEs and SAEs until the events have subsided, until values return to within the acceptable range, the investigator determines that follow-up is no longer necessary, or the subject is referred to a nonstudy physician.

The sponsor will report SAEs to the FDA and investigators according to local regulations.

Table 13–2 Reporting Requirements for Adverse Events

Reporting Requirements for Adverse Events		

13.2.2 Recording of Serious Adverse Events

All SAE information must be recorded on the SAE form provided by the Sponsor. Additional follow-up information (e.g., test results, autopsy, and discharge summary) may be requested to supplement the SAE report form and can be attached as de-identified records. A copy of all initial and follow-up reports must be filed with the subject's medical records.

14.0 STATISTICAL CONSIDERATIONS

14.1 Sample Size Determination

Up to 150 subjects will be enrolled at up to fifteen (15) investigative sites. The sample size for this study is not based on statistical considerations. The sample size was selected to ensure that 100 subjects will remain in the study for 12-months of evaluation.

14.2 Analysis Data Sets

Subjects who receive at least one dose of Gablofen® (baclofen injection) 3 mg/mL will be included in the safety analyses.

Subjects that continue on therapy and complete a 12-month course of therapy will be included in the assessment for inflammatory granulomas.

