3.3.1 Treatment of an Inflammatory Granuloma

If an inflammatory granuloma is detected early in its clinical course, depending upon an individual patient's clinical condition, intraspinal therapy may be continued after one of the following interventions:

- Withdraw the catheter to a level below the inflammatory granuloma.
- Remove the involved catheter and replace it with a new catheter positioned below the inflammatory granuloma.
- Disconnect the involved catheter from the connector (two-piece catheter), or transect the involved catheter above the level of the lumbo-dorsal fascia (one-piece catheter) leaving the intraspinal catheter segment undisturbed. Ligate the exposed end of involved catheter to prevent CSF loss. Implant a new catheter with its tip below the inflammatory granuloma, and connect the new catheter to the proximal (pump) catheter segment.

Prompt open surgical removal of the granuloma or decompression of the spinal cord should be considered in patients who have a significant or progressive neurological deficit.

Regardless of interventions, if a granuloma is detected, the subject should be discontinued from this investigational trial and treated with conventional baclofen therapy.

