14.3 Data Analyses

Data will be presented as summary statistics for each dose group and each product used. The intent-to-treat (ITT) population includes all patients who were deemed eligible, have signed the informed-consent form (ICF), have been implanted with the SynchroMed® II Programmable Pump and treated with baclofen. The evaluable (or “per protocol”) population is the subset of ITT patients who were deemed eligible, signed the ICF, have been clinically evaluated for inflammatory granuloma formation through a physical examination and evaluation of the investigator.

The incidence of inflammatory granulomas, suspected granulomas, and other catheter related events will be compared by a paired two-tailed T-test between each of the treatment groups. Results will be summarized in 9-month and 12-month interim reports and included in the overall study final report at the end of 3 years.

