2.1.1. Study Endpoints

2.1.1.1. Primary Endpoint

The primary endpoint is the rate of confirmed inflammatory granulomas after the first 12-months of therapy following the initiation of treatment with a 3 mg/mL formulation of Gablofen® (baclofen injection).

A confirmed inflammatory granuloma or mass is one where there are clinical signs and symptoms of an inflammatory granuloma, and an intradural extra-medullary mass is verified by an MRI with contrast enhancement. If only clinical signs and symptoms are identified, and no other assignable cause can be identified, the event will be recorded as a possible inflammatory mass.

All MRI-confirmed granulomas will be evaluated by a central independent radiologist as a routine trial procedure per the protocol.

Incidence is defined as the number of subjects with one or more events.

The rate of inflammatory granulomas will be evaluated based on 0 to 9 months, 0 to 12 months, and > 12 months of therapy.

For 0 to 9 months and 0 to 12 months of therapy, rate will be defined as:

$$\text{Rate} = I_T / (N_T + G_T)$$

Where:

I_T = Number of subjects with an inflammatory granuloma within the time interval

N_T = Number of subjects who reach the end of the time interval

G_T = Number of subjects with inflammatory granuloma who discontinue prior to reaching the end of the time interval

For > 12 months of therapy, rate will be defined as:

$$\text{Rate} = I_{>12} / N_{>12}$$

Where:

$I_{>12}$ = Number of subjects with an inflammatory granuloma after 12 months of therapy

$N_{>12}$ = Number of subjects who reach beyond 12 months of therapy

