6. ANALYSIS POPULATIONS

Safety Population

All subjects who were administered any amount of investigational product will be included in the analysis of safety.

Intent-to-treat (ITT) Population

The intent-to-treat (ITT) population will include subjects who were deemed eligible, have signed the informed-consent form (ICF) and treated with 3mg/ml baclofen.

Per-Protocol (PP) Population

The Per-Protocol population (PP) population will include subjects who were deemed eligible, signed the ICF, have been clinically evaluated for inflammatory granuloma formation through a physical examination evaluation of the investigator and receive therapy for at least 12 months and have no major protocol violations.

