10.3. Clinical Evaluation for Inflammatory Mass

The incidence (number of subjects with one or more events), frequency and rate of inflammatory granulomas will be summarized for 0 to 9 months, 0 to 12 months, and > 12 months of therapy. All inflammatory granulomas data will be listed for each subject and data from any SAE reports relating to inflammatory granulomas will be summarized in full detail.

A summary of the incidence and frequency of inflammatory granulomas by classification (Confirmed and possible) will also be presented.

These analyses will be performed for both the ITT and PP populations. The ITT population will be the primary analysis population.

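### Protocol 14.2 and the SAP per-protocol set lose confirmed granulomas detected before month 12, and 14.2 contradicts the SAP's ITT primary analysis, which keeps them

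*Protocol*

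**What the plan says.** **Protocol.** The primary endpoint (3.2.1) is the rate of definite granulomas in the first 12 months on the 3 mg/mL formulation. Section 14.2 puts everyone with at least one dose into the safety analyses, and then says of the granuloma assessment: "Subjects that continue on therapy and complete a 12-month course of therapy will be included in the assessment for inflammatory granulomas". Section 3.3.1 says "if a granuloma is detected, the subject should be discontinued from this investigational trial", and section 3.7 makes continued treatment conditional on the absence of a granuloma. Section 14.3 and the synopsis define an evaluable set of subjects who "have been clinically evaluated for inflammatory granuloma formation through a physical examination and evaluation of the investigator", with no minimum duration. Section 14.3 adds: "Results will be summarized in 9-month and 12-month interim reports".

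**SAP.** Section 6 defines ITT as eligible, consented and treated, with no minimum duration. It requires PP subjects to "receive therapy for at least 12 months and have no major protocol violations". Section 10.3 says of the granuloma summaries: "These analyses will be performed for both the ITT and PP populations. The ITT population will be the primary analysis population". Section 2.1.1.1 defines the 0 to 9 and 0 to 12 month rates as I_T/(N_T + G_T). Here I_T is the number of subjects with a granuloma in the interval, N_T is the "Number of subjects who reach the end of the time interval", and G_T is the "Number of subjects with inflammatory granuloma who discontinue prior to reaching the end of the time interval". Section 8.1 keeps a withdrawn subject's results up to withdrawal.

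**The concern.** Under Protocol 3.3.1 the outcome itself ends treatment. An analysis set that requires 12 months of treatment therefore removes the subjects who had the outcome early. Protocol 14.2 and the SAP's PP population both set that requirement.

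Two things are at stake. First, the documents give different analysis sets for the primary endpoint. The SAP adds early granuloma discontinuations back through G_T in ITT, and Protocol 14.2 leaves them out. Second, the PP table will stand beside the ITT table. A PP rate of 0% could be read as supporting a low ITT rate, when PP cannot show a confirmed case that was detected before month 12 and then discontinued.

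**Working it through.** **Inputs.** 100 completers at 12 months and up to 150 enrolled (Protocol 14.1). Rate formula from SAP 2.1.1.1. Background of 12 granulomas in 4,384 pump patients, all on morphine, and 0 in 1,283 on baclofen (Protocol 1.1). The documents give no expected number of cases, so the counts below are assumed. The SAP names no interval method; exact (Clopper-Pearson) 95% limits are assumed. The documents state no rate or precision figure to reproduce, and the sample size is declared not to rest on statistical considerations.

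**Step 1: follow one case.** Take a confirmed granuloma detected before month 12 in a subject who is discontinued as 3.3.1 says.
- Protocol 14.2: the subject did not complete 12 months, so the case is out.
- SAP PP: the subject had under 12 months of therapy, so the case is out.
- SAP ITT: the subject was treated and is in. The case adds 1 to I_T and 1 to G_T, so it counts in numerator and denominator.

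**Step 2: G_T within PP.** G_T for 0 to 12 months counts granuloma subjects who stop before month 12. PP admits nobody who stops before month 12. So G_T is 0 in PP, and the formula reduces to I_T/N_T among completers.

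**Step 3: size.** Let g cases be detected early, with 100 completers and no case among them.
- Completer and PP rate: 0/100 for every g. Upper limit 1 − 0.025^(1/100) = 3.62%.
- SAP formula in ITT, g/(100 + g):
  - g = 1: 1/101 = 0.99% (0.03 to 5.39)
  - g = 3: 3/103 = 2.91% (0.60 to 8.28)

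**Step 4: direction.** Now let c cases be found at the month-12 visit in subjects who count as completers. The completer rate is c/100 and the SAP rate is (c + g)/(100 + g). The SAP rate minus the completer rate is g(100 − c)/[100(100 + g)]. This is positive whenever at least one early case is lost and c is below 100, so the completer rate is then always below the SAP rate.

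Against all treated subjects the sign can change. With g = 1, c = 3 and 150 treated:
- Completers: 3/100 = 3.00%
- SAP formula: 4/101 = 3.96%
- All treated: 4/150 = 2.67%

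**Step 5: how often it matters.** At the background figure, 150 × 12/4,384 = 0.41 cases are expected. The chance of no case in 150 is (1 − 12/4,384)^150 = 66%. That figure comes from morphine patients followed from 2003 to 2010 and is applied here without adjustment for time. The Protocol itself draws no definite conclusion above 2 mg/mL.

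**The case against.** The strongest reply is that the SAP already handles this where it counts. ITT is primary, G_T restores early cases, section 8.1 keeps data up to withdrawal, and the SAP plans no completer rate of the Protocol 14.2 kind. That is correct. A reader might infer from 14.2 that the trial's primary rate excludes early granulomas; the SAP does not support that.

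Other points in the plan's favour:
- **14.2 does not say that only completers are assessed.** True. But the sentence stands under Analysis Data Sets, directly after a broader at-least-one-dose safety set, and nothing else in 14.2 defines a granuloma set. The restrictive reading is the natural one.
- **A minimum duration is common in a supportive PP set.** True. It does harm here because the outcome is itself a reason to stop.
- **Cases remain visible in adverse event tables, listings and narratives.** True, but those do not correct the PP rate or its interval.
- **The effect may be nil.** With no case, nothing is lost.

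Two stronger readings also fail. One is that the completer rate is always too low: Step 4 shows this holds against the SAP formula but not against all treated subjects. The other is that the PP rate for 0 to 9 months must be zero. SAP 2.1.1.1 does not say whether onset or MRI date places a case in an interval. A case with onset at month 8 that is confirmed at the 12-month visit could count.

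The loss concerns confirmed cases. Possible granulomas need not lead to discontinuation. Whether SAP 8.2, which excludes some unscheduled data from analysis, touches symptom-driven MRIs is a separate question.

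**Conclusion.** The point holds in this form. Where Protocol 3.3.1 is followed, confirmed granulomas detected before month 12 are lost from a Protocol 14.2 rate and from the SAP's supportive PP rate. Protocol 14.2 also contradicts the SAP's primary analysis, and it sits poorly with Protocol 14.3, the synopsis and SAP 8.1. A 12-month completer set also cannot supply the 9-month report for subjects who are between months 9 and 12.

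The planned output affected is the PP table; the primary ITT rate is not affected by this rule. With 100 completers and all cases detected early, the shortfall against the SAP formula is 0.99 percentage points for one case and 2.91 for three. These are assumed counts, and at the Protocol's background figure no case is the most likely result. It should be fixed because the conflict concerns the set for the primary endpoint and the repair is cheap.

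**What to change.** 1. **Protocol 14.2.** Replace the second sentence with: *The primary assessment for inflammatory granulomas will use the ITT population (eligible, consented and treated with 3 mg/mL baclofen); subjects who discontinue because of a granuloma are counted as cases. The per-protocol population as defined in the SAP is supportive.*
2. **SAP 6.** Change the PP duration condition to: *on therapy for at least 12 months, or discontinued earlier because of an inflammatory granuloma*. Apply it to all PP tables, including demographics, so that the PP number is the same throughout. Make the evaluable definitions in Protocol 14.3 and the synopsis match; at present they also lack the SAP's condition on major protocol violations.

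With both edits, the illustration gives g/(100 + g) in PP as in ITT. The cost is wording in the Protocol (14.2, 14.3 and synopsis) and SAP 6, with no new data or patients. No change to Protocol 3.3.1 is proposed.

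The SAP denominator N_T + G_T also leaves out subjects who leave early without a granuloma. That is a separate issue. A percentage over all treated subjects would suit the final analysis, but at the interims it would include subjects with incomplete follow-up.

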14.3 Data Analyses

Data will be presented as summary statistics for each dose group and each product used. The intent-to-treat (ITT) population includes all patients who were deemed eligible, have signed the informed-consent form (ICF), have been implanted with the SynchroMed® II Programmable Pump and treated with baclofen. The evaluable (or “per protocol”) population is the subset of ITT patients who were deemed eligible, signed the ICF, have been clinically evaluated for inflammatory granuloma formation through a physical examination and evaluation of the investigator.

The incidence of inflammatory granulomas, suspected granulomas, and other catheter related events will be compared by a paired two-tailed T-test between each of the treatment groups. Results will be summarized in 9-month and 12-month interim reports and included in the overall study final report at the end of 3 years.

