Safety Analysis (Cont.)	
Clinical signs and symptoms that may indicate an inflammatory granuloma include:
 
○ a sudden decrease in therapeutic response requiring increased daily doses that is not attributed to other assignable causes (e.g. mechanical failures, catheter movement or catheter blockages)○ unexplained pain at the dermatomal level of the catheter tip○ unexplained neurological deficit or dysfunction that could be due to compression of the spinal cord at the level of a catheter tip 
For the purpose of this study, definite inflammatory granuloma is an intramural extra-medullary mass at the catheter tip that is confirmed by an infusion MRI. If only clinical signs are detected, but the inflammatory granuloma or mass cannot be verified by MRI, and no other cause can be determined, the event will be classified as a possible inflammatory granuloma. If in the opinion of the investigator there is a reasonable probability that the subject may be experiencing an inflammatory granuloma, an MRI without and with infusion of a contrast agent will be requested. All MRIs will be assessed by a single central independent radiologist who will be blinded to the patient's history.
 
During the trial, all SAEs reported to the investigator shall be reported to the Mallinckrodt Pharmacovigilance department within 24 hours of the event being reported to the investigator. The investigator will be asked to provide details of the SAE, an assessment of severity of the event and an opinion as to relatedness to study medication or to other causes.
 
Safety data from the study will be analyzed by the nature, frequency, and severity of drug related serious adverse events for all subjects including at baseline, within study, and the end of study. Demographic information will be presented for each subject and summarized.
 
Treatment-emergent adverse events and relevant laboratory results will be summarized. Events of inflammatory granuloma's will be described both as part of the descriptive statistics, and each event will include a full narrative assessment including MRI reports, clinical interventions and outcome.
 
Data will be presented as summary statistics. The intent-to-treat (ITT) population includes all patients who were deemed eligible, have signed the informed-consent form (ICF) and treated with 3 mg/mL baclofen. The evaluable (or "per protocol") population is the subset of ITT patients who were deemed eligible, signed the ICF, have been clinically evaluated for inflammatory granuloma formation through a physical examination and evaluation of the investigator. The incidence of definite inflammatory granulomas, possible granulomas, and other catheter related events will be summarized in annual reports for 3 years.

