10.6. Pregnancies (as applicable).....	14

10.7. Other Safety Measures	14
10.7.1. Physical Examination.....	14
10.7.2. Medical History	14
10.7.3. Vital Signs.....	14
10.8. Statistical Method for Analysis of Safety and Demographic data.....	14
10.8.1. Wilcoxon Signed-rank Test.....	14
10.8.2. 95% Confidence Interval.....	15
11. REFERENCES.....	15

Trademark Information

Trademarks not owned by MALLINCKRODT PHARMACEUTICALS, INC.
SAS®

LIST OF ABBREVIATIONS

ABBREVIATION	DEFINITION
AE	Adverse event
CFR	Code of Federal Regulations
cGMP	Current Good Manufacturing Practices
CSF	Cerebral Spinal Fluid
CNS	Central nervous system
CO ₂	Carbon dioxide
CRF	Case report form
CRU	Clinical research unit
CTCAE	Common Terminology Criteria for Adverse Events (v. 4.03)
EC	Ethics Committee
ECG	Electrocardiogram
g	Gram
GABA	Gamma-aminobutyric acid
GCP	Good Clinical Practice(s)
ICF	Informed Consent Form
ICH	International Conference on Harmonization
Incidence	Number of subjects with one or more events
IRB	Institutional Review Board
IT	Intrathecal Injection
IP	Investigational Product
kg	Kilogram
L	Liter
MedDRA	Medical Dictionary for Regulatory Activities
MFD	Maximum Feasible Dose
mg	Milligram
mL	Milliliter

ABBREVIATION	DEFINITION
MRI	Magnetic Resonance Imaging
NCI	National Cancer Institute
NDA	New Drug Application
PI	Principal Investigator
Rate	Number of events adjusted for a unit of time
SAP	Statistical Analysis Plan
SAE	Serious Adverse Event
USP	United States Pharmacopeia
WHODD	World Health Organization Drug Dictionary

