10.8. Statistical Method for Analysis of Safety and Demographic data

10.8.1. Wilcoxon Signed-rank Test

The Wilcoxon signed-rank test is a non-parametric statistical hypothesis test for the case of two related samples or repeated measurements on a single sample. It can be used as an alternative to the paired Student's *t*-test when the population cannot be assumed to be normally distributed. Like the paired or related sample *t*-test, the Wilcoxon test involves comparisons of differences between measurements, so it requires that the data are measured at an interval level of measurement. However, it does not require assumptions about the form of the distribution of the measurements. It should therefore be used whenever the distributional assumptions that underlie the *t*-test cannot be satisfied. This test will be used to test the difference between baseline and visit in case the variables are continuous. SAS code such as that below will be used to fit the method described above:

```
PROC UNIVARIATE;  
  VAR chage;  
  RUN;
```

10.8.2. 95% Confidence Interval

The incidence (number of subjects with one or more events) of inflammatory granulomas, suspected granulomas, and other catheter related events will be summarized and a 95% CI of the percent of subjects with one or more events will be presented. The rate of subjects with inflammatory granulomas for 0 to 9 months, 0 to 12 months and > 12 months therapy period will be summarized including a 95% CI of the mean rates. Results will be summarized in the three planned interim reports and included in the overall study final report at the end of 3 years.

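### Protocol 14.3 specifies a paired t-test of granuloma incidence that this single-arm study cannot run; SAP 10.8.2 replaces it with 95% intervals but names no method for them

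*Protocol*

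**What the plan says.** Protocol 14.3 (Data Analyses) first states: "Data will be presented as summary statistics for each dose group and each product used". It then says that the incidence of three event types (inflammatory granulomas, suspected granulomas, other catheter-related events) "will be compared by a paired two-tailed T-test between each of the treatment groups". Dose group, product and treatment group are not defined there or elsewhere.

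Other parts of the documents describe a different plan:

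- Protocol 3.4.1 says the study is not randomized and has no concurrent controls. Protocol 3.5.1 switches every participant to 3 mg/mL.
- The protocol synopsis (Safety Analysis, continued) plans summary statistics. It says that definite and possible granulomas and "other catheter related events will be summarized in annual reports for 3 years".
- SAP 2.2 tests no formal hypotheses, and SAP 10 plans no formal analysis of safety data.
- SAP 10.8.2 takes the same three event types as Protocol 14.3 and says that "a 95% CI of the percent of subjects with one or more events will be presented". For the rates over 0 to 9, 0 to 12 and more than 12 months it says that the "therapy period will be summarized including a 95% CI of the mean rates". It names no method for either interval.

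SAP 2.1.1.1 defines each rate by a formula. For the first two periods the numerator is "Number of subjects with an inflammatory granuloma within the time interval". The denominator is "Number of subjects who reach the end of the time interval" plus the subjects with a granuloma who discontinued earlier. After 12 months it is subjects with a granuloma over subjects who go beyond 12 months.

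**The concern.** The t-test sentence covers the events that carry the primary endpoint, and it describes an analysis for which the design supplies no groups and no pairs. A reader with only the protocol would expect a test result that cannot be delivered. A reader with both documents finds a comparison in one and a descriptive summary in the other. The SAP does not say that it departs from the protocol here.

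The SAP's replacement is the right kind of analysis but is not fully specified. The protocol has no expectation of complications (1.4) and cites no granuloma among 1,283 baclofen patients in a surveillance study (1.1). With zero events the point estimate is 0% whatever the method, so the upper confidence limit carries the information. That limit depends on a method the SAP does not name.

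**Working it through.** **Inputs.** Single arm, all switched to 3 mg/mL (Protocol 3.4.1, 3.5.1). History of granuloma is an exclusion (Protocol 4.2). Up to 150 enrolled, with 100 intended to remain at 12 months (Protocol 14.1, SAP 5.1). The sample size is stated not to rest on statistical considerations, and no alpha, power or effect size is given, so there is no design figure to reproduce. Event counts below are assumed.

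**Step 1: can the t-test be run?** A paired t-test needs two measurements on the same or matched units.

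- *Between treatment groups:* there is one treatment and no matched second group.
- *Between pediatric and adult subjects* (the subgroups in Protocol 14.4 and SAP 7.3): these are independent groups, not pairs.
- *Before against after:* this is not a comparison between treatment groups. Because prior granuloma is excluded, every baseline value is 0. With no events in 100 subjects all differences are 0, their standard deviation is 0, and t = 0/0 is undefined. With one event in 100 the mean difference is 0.01, the standard deviation 0.1 and the standard error 0.1/√100 = 0.01, so t = 1.0 on 99 df and p = 0.32. The exact McNemar p for one event is 1.00. With two and three events the t-test gives 0.16 and 0.083, against 0.50 and 0.25. Even where this reading can be computed, it gives misleadingly small p-values.

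**Step 2: does another part of the SAP rescue the test?** SAP 7 and 10.8.1 keep paired t-test or Wilcoxon p-values, so the SAP is not wholly free of tests. They apply to change from baseline in continuous variables, which does not cover granuloma incidence.

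**Step 3: the interval at zero events.** With x = 0 of n and z = 1.96:

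- Wald: p ± z√(p(1−p)/n) with p = 0 gives 0 to 0% for any n. A t-interval for the mean of 0/1 data also gives 0 to 0%, because the standard deviation is 0.
- Clopper-Pearson upper limit: 1 − 0.025^(1/n).
- Wilson upper limit: z²/(n + z²), with z² = 3.84.

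| Data | Wald or mean-based | Clopper-Pearson | Wilson |
|---|---|---|---|
| 0/100 | 0 to 0% | 0 to 3.62% | 0 to 3.70% |
| 0/150 | 0 to 0% | 0 to 2.43% | 0 to 2.50% |

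**Step 4: one event.** For 1/100 the Wald interval is 1% ± 1.96 × √(0.01 × 0.99/100) = 1% ± 1.95%. Its lower limit is negative (reported as 0) and its upper limit is 2.95%. The exact interval is 0.03 to 5.45%. The Wald upper limit with one event is thus below the exact upper limit with none (3.62%).

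**The case against.** The strongest reply is that the SAP has already dealt with the main defect. SAP 10.8.2 follows the structure of the Protocol 14.3 sentence, with the same events and the same final report, and puts summaries and intervals in place of the t-test. The SAP therefore contains no t-test of granuloma incidence. This stands, and it limits the consequence. It does not remove the contradiction: the synopsis and 14.3 disagree within the protocol itself. The SAP is based on protocol version 2.0; the title pages are not available to confirm that the protocol reviewed is that version, but the internal conflict does not depend on it.

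A second reply is that the interval wording may simply be loose. That also stands. The first interval in 10.8.2 is for a percent, with no mention of a mean, and an exact method is compatible with both sentences. A reader might infer that the SAP commits to a 0 to 0% interval. It does not; it leaves that method possible.

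A further stronger reading concerns the word rate. The SAP abbreviation list gives "Number of events adjusted for a unit of time", while 2.1.1.1 uses subjects over subjects. A reader might infer that the primary endpoint is undetermined, or that the results after 12 months could differ by a large factor. The documents do not support this. SAP 2.1.1.1 gives explicit formulas for all three periods, and 10.8.2 speaks of the rate of subjects for the same periods. No analysis section uses person-time. The formulas govern over a glossary line. Any numerical gap after 12 months would mainly be a change of unit and depend on assumed follow-up: one event in 100 subjects is 1.0% as a proportion, and 2.0, 1.0 or 0.5 per 100 person-years at mean follow-up of 0.5, 1 or 2 years.

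**Conclusion.** The point holds in two parts. First, the t-test in Protocol 14.3 cannot be run as written and contradicts the synopsis and SAP 2.2, 10 and 10.8.2. This is certain from the text, but the practical risk is modest because the SAP has replaced the test. Second, SAP 10.8.2 should name its interval method. At zero events the upper limit for 0/100 is 0% under a mean-based or Wald interval and 3.62% under the exact one; for 0/150 it is 0% against 2.43%.

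These limits assume no events and use 100 and 150 as planning figures. The actual denominators are not known, and smaller ones, for example in the age subgroups, would give wider exact intervals. The choice between Clopper-Pearson and Wilson is of little consequence (3.62% against 3.70% at n = 100); what matters is excluding a method that collapses at zero. The glossary entry for rate is a minor inconsistency and no more.

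**What to change.** **Protocol 14.3.** Replace the t-test sentence with: *Incidences will be summarized with 95% confidence intervals as specified in the SAP; no between-group comparison will be made.* Delete the reference to dose groups and products from the first sentence.

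**SAP 10.8.2.** Drop the reference to mean rates and state: *Two-sided 95% Clopper-Pearson intervals will be given for the percent of subjects with events and for each rate defined in Section 2.1.1.1, including when no events are observed.* Wilson intervals would be an acceptable alternative.

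**SAP abbreviation list (minor).** Align the entry for rate with the formulas in 2.1.1.1.

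**Cost.** One protocol amendment and one SAP revision, with no added subjects, visits or data. Exact intervals are slightly conservative. The changes should be made before the results are seen.
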